6.1.3. Adverse Events of Special Interest and Clinical Importance

Adverse events of special interest will be summarized based on the following criteria:

- Central serous retinopathy (CSR):
- Growth disorder (including accelerated bone growth and SCFE) and fractures in children and adolescent subjects (≥ 6 to < 18 years of age) is an adverse event of special interest for erdafitinib.

Adverse events of clinical importance on the following criteria will be summarized:

- Eye Toxicity (excluding CSR): Dry eye, Xerophthalmia, Keratitis, Ulcerative keratitis, Conjunctivitis, Blepharitis, Cataract, Cataract subcapsular, Conjunctival haemorrhage, Conjunctival hyperaemia, Conjunctival irritation, Corneal erosion, Corneal infiltrates, Eye inflammation, Eye irritation, Eye pain, Foreign body sensation in eyes, Lacrimation increased, Night blindness, Ocular hyperaemia, Photophobia, Vision blurred, Visual acuity reduced, Visual impairment, Xanthopsia
- Hyperphosphataemia: Hyperphosphataemia
- Nail Toxicity: Nail bed bleeding, Nail discolouration, Nail disorder, Nail dystrophy, Nail ridging, Onychalgia, Onychoclasia, Onycholysis, Paronychia, Nail toxicity, Onychomadesis
- Skin Toxicity: Dry skin, Hyperkeratosis, Skin atrophy, Skin exfoliation, Skin fissures, Skin lesion, Xeroderma, Blister, Erythema, Palmar erythema, Palmar-plantar erythrodysaesthesia syndrome, Plantar erythema, Rash, Rash erythematous, Rash macular, Rash maculo-papular, Skin ulcer, Toxic skin eruption
- Gastrointestinal toxicity: Stomatitis, Dry mouth, Diarrhoea, Aptyalism, Mucosal inflammation

Note that the most up-to-date list of adverse events of special interest and adverse events of clinical importance will be used at the time of analysis.

Incidence of AEs of special interest will be summarized. The TEAE incidence rate by time to 1st onset will be calculated for the time periods 0 to 1 month, >1 month to 2 months, >2 months to 3 months and >3 months. Time to first onset of the TEAE will be summarized based on the observed TEAE values.

$$\text{Incidence rate} = \frac{\text{Number of subjects with 1}^{\text{st}} \text{ onset of TEAE}}{\text{Treated Subjects}} \text{ in the period of time}$$

Subjects who didn't have the TEAE will be censored, and the date of study completion/discontinuation will serve as the time of censoring.

6.1.4. Deaths

A summary of deaths during the treatment and up to 30 days after last dose will be provided, along with the primary cause of death. In particular, frequencies of deaths due to study treatment-related adverse events will also be reported. A death is study medication-related death if the primary cause is a drug related AE.

6.2. Clinical Laboratory Tests

Laboratory data of hematology and serum chemistry up to 30 days after last dose or the end of treatment visit date, whichever is later, will be reported in SI units.

Applicable laboratory results will be graded according to NCI-CTCAE version 5.0.

The following laboratory tests may be analyzed:

- Hematology: hemoglobin, platelet count, WBC count, ANC
- Chemistry: ALT, chloride, albumin, creatinine (including calculated creatinine clearance), alkaline phosphatase, magnesium, AST, bicarbonate, phosphate, blood glucose, potassium, sodium, total bilirubin, total protein, calcium,
- Parathyroid hormone (PTH)
- TSH (adolescents only): Thyroid stimulating hormone, free thyroxine (T4), and total triiodothyronine (T3)
- IGF-1 (adolescents only)

Descriptive statistics will be calculated for each laboratory analyte at baseline and at each scheduled time point. Changes from baseline results will be presented in pre- versus post-intervention cross-tabulations (with classes for below, within, and above normal ranges). Frequency tabulations of the abnormalities will be made. A listing of subjects with any laboratory results outside the reference ranges will be provided. Parameters with predefined NCI-CTCAE toxicity grades will be summarized. Change from baseline to the worst adverse event grade experienced by the subject during the study will be provided as shift tables.

Liver function abnormality by Hy's Law: For subjects with any elevated liver enzyme (AST or ALT) of $>3\times\text{ULN}$, ALP $<2\times\text{ULN}$, and associated with an increase in bilirubin (total) $\geq 2\times\text{ULN}$, a listing for all subjects with all such records will be provided and a summary table of the number of such subjects will be provided.

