6.5. Concomitant Therapies

Concomitant therapies must be recorded at the time of full-study screening, during the study, and up to 30 days after the last dose of study drug. All therapies (prescription or over-the-counter medications) continued at the start of the study or started during the study and different from the study drug, including prior anticancer therapy, must be recorded in the CRF.

Caution should be exerted for subjects taking anti-coagulant therapies (see Section 6.5.3). Frequent monitoring for international normalized ratio (INR) is allowed at the treating physician's discretion. The sponsor must be notified in advance, or as soon as possible thereafter, of any instances where prohibited medications are administered.

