8.4. Adverse Events and Serious Adverse Events

Timely, accurate, and complete reporting and analysis of safety information from clinical studies are crucial for the protection of subjects, investigators, and the sponsor, and are mandated by regulatory agencies worldwide. The sponsor has established Standard Operating Procedures in conformity with regulatory requirements worldwide to ensure appropriate reporting of safety information; all clinical studies conducted by the sponsor or its affiliates will be conducted in accordance with those procedures.

Adverse events will be reported by the subject (or, when appropriate, by a caregiver, surrogate, or the subject's legally acceptable representative) for the duration of the study.

8.4.1. Time Period and Frequency for Collecting Adverse Event and Serious Adverse Event Information

All Adverse Events

All adverse events and special reporting situations, whether serious or non-serious, will be reported from the time a signed and dated Full-study ICF is obtained until 30 days after the subject's last dose of study drug. Serious adverse events, including those spontaneously reported to the investigator within 30 days after the last dose of study drug, must be reported using the Serious Adverse Event Form. The sponsor will evaluate any safety information that is spontaneously reported by an investigator beyond the time frame specified in the protocol.

Serious Adverse Events

All serious adverse events occurring during the study must be reported to the appropriate sponsor contact person by study-site personnel immediately but no later than 24 hours of their knowledge of the event.

Information regarding serious adverse events will be transmitted to the sponsor using the Serious Adverse Event Form, which must be completed and signed by a physician from the study site, and transmitted to the sponsor within 24 hours. The initial and follow-up reports of a serious adverse event should be made by facsimile (fax).

A possible Hy's law Case is defined by the occurrence of ALT/AST $\geq 3 \times$ ULN, alkaline phosphatase $\langle 2 \times$ ULN together with total bilirubin $\geq 2 \times$ ULN or INR ≥ 1.5 (if measured). Any possible Hy's Law case is considered an important medical event and should be reported as an SAE to the sponsor in an expedited manner (Appendix 10.2), even before all other possible causes of liver injury have been excluded.

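### SAP 6.2 counts Hy's Law cases on narrower criteria than protocol 8.4.1: the INR limb is missing and the transaminase cut-off is strict rather than inclusive

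*SAP*

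**What the plan says.** Protocol 8.4.1 gives the definition: "A possible Hy's law Case is defined by the occurrence of ALT/AST $\geq 3 \times$ ULN", with ALP below 2×ULN, together with either total bilirubin at or above 2×ULN "or INR ≥ 1.5 (if measured"). It then sets the consequence: "Any possible Hy's Law case is considered an important medical event and should be reported as an SAE to the sponsor in an expedited manner". Protocol Appendix 2 (10.2) refers the reader back to 8.4.1 for these requirements.

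SAP 6.2 has a Hy's Law paragraph of its own. It selects subjects with AST or ALT above 3×ULN and ALP below 2×ULN, "associated with an increase in bilirubin (total") at or above 2×ULN. It plans a listing of these subjects, and "a summary table of the number of such subjects will be provided". INR is not mentioned there or in the SAP's list of laboratory tests.

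INR is also absent from the scheduled panels in Protocol Appendix 2. Protocol 6.5, in its paragraph on anticoagulants, says only: "Frequent monitoring for international normalized ratio (INR) is allowed at the treating physician's discretion". Protocol 6.6 asks for coagulation parameters to be followed in cases of impaired wound healing, imminent surgery or possible bleeding.

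**The concern.** Two documents use the same name for two different sets of subjects. The protocol set triggers expedited SAE reporting, while the SAP set is tabulated. If the SAP set is smaller, the study can hold a possible Hy's Law SAE that its own Hy's Law table does not count, and neither document has a rule to explain or reconcile the difference.

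This paragraph is the only liver-specific output in the SAP. The events of special interest and of clinical importance in SAP 6.1.3 contain no hepatic category, and serious TEAEs are shown by system organ class and preferred term, so no other planned output identifies a subject as a possible Hy's Law case.

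The population makes the question a practical one. Inclusion criterion 9.3 admits subjects with liver metastases at ALT/AST up to 5×ULN. Cholangiocarcinoma alone is planned at about 30 Broad Panel plus about 30 Expansion subjects.

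**Working it through.** The plan states no figure to reproduce. The check is whether one rule is contained in the other.

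| Element | Protocol 8.4.1 | SAP 6.2 |
|---|---|---|
| ALT or AST | ≥3×ULN | >3×ULN |
| ALP | <2×ULN | <2×ULN |
| Total bilirubin | ≥2×ULN | ≥2×ULN |
| INR alternative to bilirubin | ≥1.5, if measured | none |

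1. As logical rules:
   - Protocol: ALT/AST ≥3 and ALP <2 and (bilirubin ≥2 or INR ≥1.5).
   - SAP: ALT/AST >3 and ALP <2 and bilirubin ≥2.

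   Any profile that meets the SAP rule also meets the protocol rule. The reverse fails in two places: INR-only cases, and ALT/AST at exactly 3×ULN.

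2. To confirm this, both rules were applied to a grid around the cut-offs, in multiples of ULN except for INR: ALT/AST 2.9, 3.0, 3.1, 8; ALP 1.0, 1.9, 2.0, 3; bilirubin 0.8, 1.9, 2.0, 4; INR not measured, 1.0, 1.49, 1.5, 2.5. That is 4 × 4 × 4 × 5 = 320 profiles.
   - Bilirubin/INR pairs meeting the protocol: 2 × 5 = 10 through bilirubin, plus 2 × 2 = 4 through INR alone, giving 14.
   - Protocol rule: 3 × 2 × 14 = 84 profiles.
   - SAP rule: 2 × 2 × 10 = 40 profiles.
   - Protocol only: 84 − 40 = 44. SAP only: 0.

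3. Split of the 44:
   - INR omission alone (ALT/AST >3, bilirubin <2, INR ≥1.5): 2 × 2 × 4 = 16.
   - Strict sign alone (ALT/AST exactly 3, bilirubin ≥2): 1 × 2 × 10 = 20.
   - Both reasons: 1 × 2 × 4 = 8.
   - Sum: 16 + 20 + 8 = 44.

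These are grid cells chosen to sit on the boundaries. They show containment and say nothing about how many subjects would be affected. The documents give no rate for such cases, so no expected count can be calculated.

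4. History: Protocol Appendix 14 records that the Hy's Law definition entered with Amendment 3 (August 2021). The SAP version history says that version 4 (August 2022) aligned some language with that amendment. The Hy's Law rule in the current SAP still differs, and no other SAP section restores the INR limb.

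**The case against.** The strongest defence is that 8.4.1 is a site reporting trigger for possible cases, not an analysis definition. Protocol 9.4.7 contains no Hy's Law analysis, and Section 9 leaves analysis detail to the SAP. A broad trigger and a narrower tabulation can coexist. That holds in principle, but the SAP does not say it chose a narrower rule. It uses the same label and offers no reason.

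A second objection is that the INR limb may add noise. Protocol 6.5 raises INR monitoring in connection with anticoagulants, so available values may come largely from subjects whose INR is raised by medication, and some of them may have entered with raised transaminases. This stands as a caution. However, 8.4.1 requires reporting before other causes are ruled out, so the table can list the same possible cases and leave attribution to the listing and narratives.

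Third, the difference between > and ≥ matters only at exactly 3×ULN. That is correct; the INR limb is the substantive gap.

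A reader might infer three stronger things that the documents do not support:

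- **That cases will be missed.** INR is unscheduled, so the number may be zero.
- **That liver cases would be lost to safety analysis.** They are reportable as SAEs and should appear among the serious TEAEs (SAP 6.1.1) if they fall in the TEAE period. Abnormal transaminases also appear in the out-of-range listing and shift tables of SAP 6.2.
- **That the table would always fall short of the SAE reports.** SAP laboratory data run to the later of 30 days after last dose and the End-of-Treatment visit, which may fall at 30 (+7) days. SAE collection ends at 30 days. The table could therefore include a laboratory case up to 7 days beyond the SAE window.

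Nor do the documents treat this count as a headline safety result.

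**Conclusion.** The point holds as an inconsistency of minor weight. Applied exactly as written, the SAP rule is a strict subset of the protocol rule. Any subject who qualifies only through INR, or at exactly 3×ULN, would be absent from the Hy's Law listing and count while being reportable as a possible Hy's Law SAE. The number of such subjects is unknown and may be small or zero.

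The conclusion rests on reading both definitions literally. The INR part further assumes that some subjects have an INR measured and that the value is recorded; the documents show neither how often INR will be measured nor that it is captured in the database. Subject-level safety reporting is not affected.

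**What to change.** - Restate the rule in SAP 6.2 as ALT or AST ≥3×ULN, ALP <2×ULN, and total bilirubin ≥2×ULN or INR ≥1.5 where measured.
- Label the listing and table as possible Hy's Law cases, the term used in protocol 8.4.1.
- Show in the listing which limb each subject met (bilirubin, INR or both) and any anticoagulant use, so that INR-only cases can be judged.
- Confirm that unscheduled and local INR values are captured in the database. If they are not, state that limitation beside the table.
- Reconcile the count with the Hy's Law SAE reports, noting the different end dates of the two data windows.

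The cost is a short SAP text change and minor programming, with somewhat more work if INR is not yet in the database. The downside is that some INR-qualified cases may reflect anticoagulants rather than liver injury; the added listing columns are there to make that visible. No treatment or visit rule changes.

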6.2.1. Creatinine Clearance

Cockcroft-Gault Formula for Estimated Creatinine Clearance for adults shown below will be used to derive creatinine clearance for adults. For adolescents and children, no derivation will be conducted but using the collected creatinine clearance.

$$\text{eCR} = \frac{(140-\text{Age}) \times \text{Mass (Kilograms)} \times [0.85 \text{ if female}]}{72 \times \text{Serum Creatinine (in mg/dL)}}$$

for males, the factor is 1 instead of 0.85.

OR

$$eCcr = \frac{(140-Age) \times \text{Mass (Kilograms)} \times \text{Constant}}{\text{Serum Creatinine (in } \mu\text{mol/L)}}$$

Where Constant = 1.23 for men and 1.04 for women

Reference: <http://www.mdcalc.com/creatinine-clearance-cockcroft-gault-equation/>

6.3. Ophthalmologic Examination

Summary statistics will be tabulated for the treated subjects whose results of ophthalmologic examinations were obtained from both before and after the study treatment. These summaries will include measures of change from baseline, frequency and percentage shifting from baseline, time to certain eye exam parameters, etc. Listings of treatment-emergent AEs related to the eye toxicity will also be generated.

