History of seizure and physical examination	During Screening Phase, complete physical examination including neurological examination, height, and weight. During Treatment Phase, limited physical examination of affected organs, neurological examination including record of seizure activity (subjects with primary CNS tumors, CNS metastases or other subjects at the investigator's discretion, only) and weight; record new abnormalities as AE. If examination occurs more than 7 days prior to the first dose of study drug, it must be repeated on C1D1 prior to dosing.		x		x		x	x	
Vital signs	Check temperature, heart rate, systolic and diastolic blood pressure; record all clinically significant abnormalities as AE.		х		X		x	х	
ECOG performance status			÷	х	Х		х		
Urine or serum β- hCG pregnancy test	Females of childbearing potential only. Screening test within 7 days prior to the first dose, or at C1D1 prior to the first dose.			-7 days	Day 1 of every cycle from Cycle 2		x		
12-lead ECG	Record postdose ECGs (see Section 8.3.3 for exact timing). May be performed more often as clinically indicated. Please conduct ECGs preferably at the same time each day at each visit (at which an ECG is conducted).	(L	х		C2D1		C4D1		
Ophthalmologic exam	To be performed by an ophthalmologist, for exact assessments see Section 8.3.5.		Х						
Amsler Grid Test	To be performed by treating physician or nurse (as directed by specific site instructions).		х		C2D1 C3D1		x	x	

			Treatment P	hase ^g (21-		-				
	NOTES	Screening Phase			Cycles 1, 2		Cycle 4+	End of	Follow-	
Parameter		Molecular Eligibility Screening Period Sc		study ng Period	Day 1	Day 14	Day 1	Treatment Visit ⁹	Up Phase ^g	
Visit Window		NA	-30 days	-14 days	C1: -3 days to D1 C2, C3: -2	+2 days	-2 to +2 days	30 (+7) days after last dose ^a	every 12 weeks± 7 days	
	y Assessments: Results (except parathyroid hormone) must be available prior to dosing testing should be available for comparison as clinically necessary.	at C1D1 and subjects sh	nould cont	inue to mee	et eligibili ty requ	uirements p	er the Inclusio	n/Exclusion c	iteria.	
Hematology	May be performed within 3 days prior to D1 of each cycle (Section 10.2)			X	Х	X	Х	Х	1	
Chemistry	May be performed within 3 days prior to D1 of each cycle (Section 10.2)			Х	Х	Х	Х	Х		
Parathyroid hormone (PTH)	May be performed within 3 days prior to D1 of each cycle (Section 10.2)			х	x	х	X (every 3rd cycle after C6)	х		
Efficacy Assessme	ents	2								

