8.3.5. Ophthalmologic Examination

All subjects must have an ophthalmologic examination performed at Screening by an ophthalmologist, which should include assessment of visual acuity, fundoscopy (examination of both central and peripheral zones should be performed), and slit lamp biomicroscopy; an Optical Coherence Tomography (OCT) must also be performed at Screening (see the OCT Manual for details). The Amsler grid test will also be administered by the treating physician or nurse at Screening. A follow-up examination should be performed as clinically necessary based on the findings of the Amsler grid tests and clinical assessment, or at regular intervals as deemed necessary by the screening ophthalmologist.

When CSR/retinal pigment epithelial detachment (RPED) is suspected, or fundoscopic retinal abnormalities are observed, as well as each time ocular adverse events lead to the subject being referred to an ophthalmologist, an OCT should be performed. Fluorescein angiography could be considered appropriate in conditions such as suspected retinal vein occlusion (RVO). In subjects with suspected retinal pathology such as CSR or RVO, a consultation with a retina specialist should be considered.

All images of the OCT scan and fluorescein angiography (if performed) must be stored in the subject's records and a redacted copy sent to the sponsor-selected central vendor for possible future independent assessment. If only a PDF is available, please review with sponsor prior to enrollment (refer to the central vendor manual).

Amsler grid (Section 10.9) testing will be administered to all subjects at Screening and during the treatment phase according to the Schedule of Activities. Observation of wavy, broken or distorted lines, or a blurred/missing area of vision is equivalent to a positive Amsler grid test. For any positive Amsler grid test, subject should be referred for full ophthalmologic examination within 7 days. However, if the subject has an abnormal Amsler grid test and otherwise normal ophthalmologic exam at baseline (during Screening), then a repeat ophthalmologic examination would be recommended only if, in the opinion of the investigator, there is a likelihood of significant change from the subject's baseline Amsler grid test at Screening, or the subject has developed new clinical symptoms.

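### Eye-exam shift percentages and time to eye finding are planned only in re-examined subjects, a group selected largely by suspected eye problems, so they are conditional figures and not incidences among treated subjects

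*SAP*

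**What the plan says.** SAP 6.3 defines who enters the eye-exam summaries: "Summary statistics will be tabulated for the treated subjects whose results of ophthalmologic examinations were obtained from both before and after the study treatment". Besides change from baseline, those summaries include "frequency and percentage shifting from baseline, time to certain eye exam parameters". No other denominator is named, and there is no category for subjects without a later exam. SAP section 6 makes the safety analysis set the default for safety analyses unless something else is specified. Here something else is specified.

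The baseline exam is universal. Protocol 8.3.5 states: "All subjects must have an ophthalmologic examination performed at Screening by an ophthalmologist". The ophthalmologic exam rows in both Schedules of Activities (Protocol 1.3 and 1.4) are marked at Screening only, whereas the Amsler grid is repeated on treatment.

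Later exams have several routes:
- Protocol 8.3.5: "A follow-up examination should be performed as clinically necessary based on the findings of the Amsler grid tests and clinical assessment".
- The same sentence continues with a route that does not depend on symptoms: "or at regular intervals as deemed necessary by the screening ophthalmologist".
- Protocol 8.3.5 again: "For any positive Amsler grid test, subject should be referred for full ophthalmologic examination within 7 days".
- Protocol 6.6.1.5 and Table 15 send subjects with new, clinically significant eye symptoms for evaluation and ophthalmologic referral.

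Neither document gives the expected share of subjects re-examined.

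**The concern.** Requiring a before and an after value does little harm when every subject has scheduled on-treatment measurements, as with laboratory tests and ECGs here. The ophthalmologic exam has no scheduled on-treatment visit. The same requirement then selects subjects largely because an eye problem was suspected.

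Two outputs are affected. A shift percentage in this subset looks like an incidence but answers a different question: how often an exam that somebody had reason to order showed a change. The time-to-finding summary has the same problem. A subject enters it only by having a later exam, so subjects never re-examined contribute no finding-free time.

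Central serous retinopathy is a named risk and an adverse event of special interest (Protocol 2.3 and 8.4.7). As planned, the report would show eye findings on two denominators, re-examined subjects in SAP 6.3 and treated subjects in SAP 6.1.3, and nothing in SAP 6.3 requires the difference to be explained.

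**Working it through.** The plan gives no figure to reproduce, so the check is algebra with a range of assumed values.

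**Inputs.** N = 240, the approximate planned size of the Broad Panel Cohort (SAP 1.4), used for illustration only; the ratios do not depend on it. Three quantities are not in the documents and are assumed: f, the share of treated subjects with a post-baseline exam; s, the share of all true shifts that are found at such an exam; and p, the true percentage shifting among all treated subjects. The observed count k = 24 is also an assumption.

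**Comparison 1: same observed count, two denominators.** The subset percentage is k/(fN) and the all-treated percentage is k/N, so the ratio is 1/f.

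| f | Re-examined | 24 over re-examined | 24 over 240 | Ratio 1/f |
|---|---|---|---|---|
| 0.2 | 48 | 50.0% | 10.0% | 5.0 |
| 0.3 | 72 | 33.3% | 10.0% | 3.3 |
| 0.5 | 120 | 20.0% | 10.0% | 2.0 |
| 0.8 | 192 | 12.5% | 10.0% | 1.25 |

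**Comparison 2: against true incidence.** The subset percentage is p × s/f, so its ratio to p is s/f, whatever p is.

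| f | s = 1 | s = 0.75 | s = 0.5 |
|---|---|---|---|
| 0.2 | 5.0 | 3.75 | 2.5 |
| 0.3 | 3.3 | 2.5 | 1.67 |
| 0.5 | 2.0 | 1.5 | 1.0 |
| 0.8 | 1.25 | 0.94 | 0.625 |

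A ratio of at least 2 needs f ≤ s/2, that is 50%, 37.5% or 25% for s = 1, 0.75 or 0.5. A ratio of at least 3 needs f ≤ s/3, that is 33%, 25% or 17%.

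**Direction.** The ratio exceeds 1 exactly when s > f, meaning that subjects with a true shift are re-examined more often than treated subjects in general. Referral for a positive Amsler grid or for symptoms pushes that way. Shifts without symptoms that are never examined lower s, and interval exams ordered by the screening ophthalmologist raise f. Both pull the ratio down.

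**The all-treated figure is not the true rate either.** It equals p × s. With p = 10% and s = 0.5 it shows 5%. It is a lower bound, because it counts every subject not re-examined as unshifted.

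**Time to finding.** The subset omits a share 1 − f of treated subjects: 80% at f = 0.2 and 20% at f = 0.8.

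**The case against.** The strongest reply is that incidence of eye toxicity is already planned properly elsewhere. SAP 6.1.3 summarises central serous retinopathy as an adverse event of special interest, divides by treated subjects, and handles time to first onset with censoring of subjects who have no event. Other eye toxicity is tabulated as an adverse event of clinical importance. Protocol 6.6.1.5 requires confirmed new retinal abnormalities to be reported as adverse events. This stands: the adverse-event tables are sound on this point, and the problem is confined to the exam-based tables in SAP 6.3.

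Second, paired change-from-baseline measures need both exams. This also stands, and those summaries may stay in the re-examined subset.

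Third, re-examined subjects are not all cases. Interval exams are allowed without symptoms, and Table 15 provides for referrals that find no eye toxicity. This weakens any claim about size, but it does not turn the subset into a sample of all treated subjects.

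Fourth, these are descriptive tables that no hypothesis or decision rule uses. That is true, and it limits the weight of the point. It does not make a conditional percentage readable as an incidence.

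**Conclusion.** The point holds for two items in SAP 6.3: the shift percentages and the time-to-finding summary. As written, both are conditional on a post-baseline exam that is largely for cause. The percentages probably overstate incidence among treated subjects, by an amount that the documents do not determine. The ratio is 1/f against the same observed count and s/f against true incidence. Both rest on assumed values of f and s.

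A reader might infer that the percentages are inflated several-fold. The documents do not support that: they give neither f nor s, and over the values tabulated above the ratio to true incidence runs from 0.625 to 5.0. A reader might also infer that nearly all event-free time is lost from the time-to-finding analysis. That too depends on the unknown f. Nor is the planned adverse-event incidence of central serous retinopathy or other eye toxicity distorted.

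This is a reporting defect on a named safety risk. It is worth correcting and has no bearing on the primary endpoint.

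**What to change.** Amend SAP 6.3 and its table shells as follows:

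1. Report the number and percentage of treated subjects with a post-baseline ophthalmologic exam, with the reason for the exam where captured.
2. Show shift counts over all treated subjects with a baseline exam, with *no post-baseline exam* as its own row and a note that the resulting percentage is a lower bound.
3. Label any percentage restricted to re-examined subjects as conditional on a post-baseline, largely for-cause exam. Paired change-from-baseline summaries may stay in this subset.
4. Run time to finding in all treated subjects with a baseline exam, censoring those without a finding at the end of the treatment-emergent period defined in SAP 6.1.2.
5. State whether an exam after study treatment means after the first dose or after treatment has ended. The Schedules mark no end-of-treatment ophthalmologic exam.

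The cost is SAP wording and slightly more table work, with no new examinations. The downside is that the all-treated figure may understate findings without symptoms, which is why the separate row and the lower-bound note are needed.
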